8.3. Exclusion criteria

- History of uveitis
- Ocular pathology or history that could influence the biometry of the effective lens position, such as ocular trauma with zonulolysis, congenital iris- or lens defects etc.
- Any eye condition influencing the lens position (to be specified) according to the investigator

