4. CLINICAL INVESTIGATION SUMMARY

Title	CT Lucia 601 IOL implantation in the sulcus
Reference Number (Acronym)	CLuS
Clinical phase	Post-marketing study (phase 4)
Objectives	To perform a retrospective investigation of the CT Lucia 601 IOL implantation in the sulcus

Endpoints	Primary endpoint: determine whether the CT Lucia 601 IOL can be used safely in the sulcus
Design	Non-commercial (academic with study grant), monocentric, post-interventional observational without use of a study drug
Data Collection	A single late-postoperative visit, scheduled ≥ 6 months after the vitrectomy See Study Flow Chart 7.3
Planned Clinical investigation Period	2019-2020
Clinical investigation population	Patients who had an implantation of the CT Lucia 601 lens
Number of Participants	100
Inclusion/Exclusion Criteria	
Inclusion criteria
 
 • Patients with an implantation of a CT Lucia 601 lens for different reasons: 
 ○ During vitrectomy to treat a complicated cataract surgery and had the implantation of a CT Lucia 601 IOL in the sulcus or patients ○ During phaco surgery with a posterior capsule tear that necessitated the implantation of the implant lens in the sulcus ○ Explantation of an in-the-bag lens and implantation of a CT Lucia 601 as replacement lens (e.g. to treat opacification of the implant lens or intolerance of the implant lens). • Age : > 18 years • Signed informed consent • Preoperative myopia less than 10 diopters • Implantation of the CT Lucia IOL at least six months earlier 
Exclusion criteria
 
 • History of uveitis • Ocular pathology or history that could influence the biometry of the effective lens position, such as ocular trauma with zonulolysis, congenital iris- or lens defects etc. • Any eye condition influencing the lens position (to be specified) according to the investigator
Device Name	CT LUCIA hydrophobic C-loop IOL: CT Lucia® 601P (hydrophobic acrylic with heparin coated surface)

Principle Intended Use	All devices are CE marked and used within their claimed intended use. In general, all devices are intended to be used during ophthalmic surgery.
Manufacturer Name	CT LUCIA 601P

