A few older PMMA IOL types are available that are on-label certified for use in the sulcus. However, since the use of these IOLs requires a large incision in the eye and are not preloaded, the use of these lenses is not up to the standard-of-care in modern lens surgery.

In our center, we have been using the IOL "PolyAI" from Physiol, that was certified for use in the sulcus. However, when production of this IOL was discontinued a few years ago, we had to look for a suitable alternative. At that time, a review of the commercially available

IOLs was performed, and it was decided that the IOL "CT Lucia 601" from Zeiss had all the properties that we considered as important for in-the-sulcus implantation, in spite of the lack of an official "in the sulcus" label. Also since we could not find any foldable and preloaded IOL that was officially labeled as "sulcus-IOL", we have implanted this IOL in the sulcus in ~150 patients with complicated cataract surgery. During the surgery, we found that this IOL had even better handling properties compared to the PolyAI that facilitate the in-the-sulcus positioning. It unfolds very slowly after insertion in the eye, allowing the surgeon to accurately place the IOL haptics in the desired position. Also during the postoperative visits, we assessed a very good centration and positioning of this CT Lucia 601 IOL.

Unfortunately, the IOL manufacturer (Carl Zeiss) decided last year to change the design of the CT Lucia 601, referred to as CT Lucia 611. Although this new design allows easier implantation in the bag, it makes the IOL in our evaluation less suitable for in-the-sulcus implantation. This concern was reported to and discussed with Zeiss. We have suggested to perform a post-implantation analysis study to objectively evaluate the use of the CT Lucia 601 IOL as a sulcus lens. Zeiss has agreed to continue the delivery of the CT Lucia 601 for this purpose.

Study expenses

Besides the examinations collected during the long-term postoperative visit, no additional study examinations are required outside of the normal standard-of-care.

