6. OBJECTIVES

The purpose of the study is to collect data that are parameters of post-IOL implantation safety:

- Questionnaire on subjective quality of vision
- Centration and anteroposterior position of the IOL (using biometry)
- Presence and quantification of any inflammation or pigment present in the anterior chamber (flare meter)
- Refractive outcome, with calculation of customized A-constant of the CT Lucia 601 IOL in-the-sulcus and quantification of higher-order aberrations (HOA)
- General safety-parameters:
 - Visual acuity
 - Intra-ocular pressure
 - Presence of macular edema or retinal nerve fiber layer (RNFL) thinning (SD-OCT)
 - Any adverse ophthalmic events

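### Exclusion 3 leaves conditions influencing lens position to the investigator's judgement at least six months after surgery, is not limited to pre-implantation conditions, and lens position is itself a safety parameter

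*Combined protocol and SAP*

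**What the plan says.** The third exclusion in section 8.3, repeated in the section 4 summary, is "Any eye condition influencing the lens position (to be specified) according to the investigator". It has no list of conditions and no reference date. The second exclusion begins "Ocular pathology or history that could influence the biometry of the effective lens position, such as ocular trauma with zonulolysis, congenital iris- or lens defects" and ends with an open-ended et cetera. Both are study-entry criteria.

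The primary endpoint in section 4 reads "Primary endpoint: determine whether the CT Lucia 601 IOL can be used safely in the sulcus". Section 6 introduces its list with "The purpose of the study is to collect data that are parameters of post-IOL implantation safety", and one item on that list is "Centration and anteroposterior position of the IOL (using biometry"). Section 11.1 adds aberrometry and attributes the higher-order aberrations it measures to tilt or decentration of the lens.

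On timing, section 7 enrols patients after the intervention, and section 8.2 requires at least six months since implantation. Section 5 reports of the existing series: "Also during the postoperative visits, we assessed a very good centration and positioning of this CT Lucia 601 IOL".

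Section 13.7, on inclusion in the analysis, says only who will be contacted. It defines no safety set, and no section describes a count of excluded patients.

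**The concern.** An eligibility rule should not depend on the outcome it helps to measure. Exclusion 3 is phrased in terms of lens position, lens position is a safety parameter, and the judgement is made when the lens has been in the eye for at least six months. A decentred or tilted lens, or a pupil caught behind the optic, could be read as evidence of a condition influencing lens position, and the eye could be left out on that ground.

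Such an eye leaves both numerator and denominator of the position, aberration and adverse-event results. The study has no randomised comparison that would share the loss between groups, and its primary question is whether sulcus placement is safe. Eyes never enrolled cannot be recovered in the analysis. The missing-data procedure in section 13.5 deals with missing outcomes, not with patients kept out at entry.

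**Working it through.** **No planned figure to reproduce.** Sections 8.1 and 13.2 give 100 participants (in total, and by group, respectively) without an event rate, precision target or power. The point rests on the wording and does not depend on that number.

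**The sections side by side.**

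1. Is lens position an outcome? Yes. Section 6 lists it as a safety parameter, and section 11.1 links aberrations to it.
2. Is exclusion 3 limited to the preoperative state? No. Neither 8.3 nor section 4 gives a date or a list.
3. Can position be known when eligibility is judged? In part. Section 5 shows that the centre looked at position at routine visits, so gross malposition could be known. The study's own measurements come later, at the study visit. Section 9.2 has consent signed at that hospital appointment, and section 9.4 withdraws incorrectly enrolled patients from further assessment, so an eligibility ruling could still be made at or after the visit.
4. Does another section close the gap? No. Section 13.7 sets no analysis population, section 14.2 provides no steering or data monitoring committee, and monitoring under 14.4 is conditional.

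**Illustration of size (all rates assumed).** Let p be the true malposition rate among otherwise eligible eyes and f the share of malpositioned eyes removed under exclusion 3. Suppose that no well-placed eye is removed. Then

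observed rate = p(1 − f) / [p(1 − f) + (1 − p)].

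For p = 5% and f = 50%: 0.025 / (0.025 + 0.95) = 0.025 / 0.975 = 2.6%.

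| True rate p | f = 0 | f = 50% | f = 75% | f = 100% |
|---|---|---|---|---|
| 3% | 3.0% | 1.5% | 0.8% | 0 |
| 5% | 5.0% | 2.6% | 1.3% | 0 |
| 10% | 10.0% | 5.3% | 2.7% | 0 |

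The chance of seeing at least one malposition in 100 eyes is 1 − (1 − observed rate)^100. For p = 5% it is 99.4% with f = 0, 92.6% with f = 50%, 72.9% with f = 75%, and 0 with f = 100%.

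**What a clean result would mean.** With 0 malpositions in 100, the exact two-sided 95% upper limit is 1 − 0.025^(1/100) = 3.6%. That limit describes eyes that passed the exclusions, not all eyes implanted.

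**Direction.** If a share g of well-placed eyes is also excluded, the second term of the denominator becomes (1 − p)(1 − g). The observed rate falls below p whenever f exceeds g. That is the expected pattern if a visibly poor position prompts the judgement.

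**Room for it to happen.** Section 5 mentions about 150 patients already implanted in the sulcus. If that were the whole pool, enrolling 100 would leave 150 − 100 = 50 (33%) outside for any reason, including refusal and non-contact. Excluded patients could be replaced, so the planned 100 could be reached with no visible shortfall.

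**The case against.** The best defence is that exclusion 3 names a cause, not a result. It removes eyes whose condition would displace any lens, so that measured position reflects the device. Read with exclusion 2, whose examples are trauma with zonulolysis and congenital defects, it may well be meant for pre-existing anatomy. The words in brackets suggest that the condition must be named, and sections 9.3 and 13.7 say all recipients will be approached, so the pool is not hand-picked. This is a reasonable account of intent. But the text sets no such limit, and naming a reason does not return the eye to the safety data.

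Several stronger readings are tempting, and the documents do not support them.

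- *The exclusions exist to protect the A-constant.* Section 6 mentions that calculation once, within "Refractive outcome, with calculation of customized A-constant of the CT Lucia 601 IOL in-the-sulcus and quantification of higher-order aberrations (HOA", and no section gives it as the reason for either criterion.
- *Exclusion 2 is equally at fault.* Its named examples are prior history or anatomy. They mainly narrow the population to which the results apply. Only its open ending shares the problem.
- *Exclusion 3 contradicts the capsule-tear route in 8.2.* A specifically named inclusion is not cancelled by a general exclusion.
- *The team already knows how every lens sits.* Section 5 gives a general impression from routine visits, not a measurement for each eye.
- *Nothing would be visible afterwards.* The condition is apparently to be specified, so some record may exist. What the plan lacks is a commitment to report it.

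**Conclusion.** The point holds for exclusion 3. As written, it permits selection on a listed safety parameter, and no other section repairs this. The likely direction is towards too few malpositions, with aberration and adverse-event results affected in the same way. This assumes that malpositioned eyes are more likely to be excluded than well-placed ones.

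The size cannot be determined from the documents. The fall from 5% to 2.6%, or to 0, rests on assumed rates and assumed exclusion shares, and total exclusion is the extreme case. A reader might infer that a few exclusions would reverse the study's conclusion. That cannot be said, because the plan defines no safety event or threshold and so has no decision rule to reverse. What can be said is that the reported rate could change materially. This is an inexpensive improvement to the wording, and there is no evidence that eyes have been or will be left out for this reason.

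**What to change.** In section 8.3 and the section 4 summary:

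1. Limit exclusion 3 to a named list of conditions documented in the chart before the CT Lucia implantation. Replace the open ending of exclusion 2 with a closed list on the same basis. Its named pre-existing conditions may stay as entry criteria.
2. Have eligibility under both criteria decided from the preoperative chart, without the postoperative position data.
3. State that postoperative findings such as decentration, tilt or pupil entrapment are outcomes and never grounds for exclusion or later withdrawal.
4. In section 13.7, commit to reporting how many implanted patients were excluded, with the reason for each.

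The cost is a few lines of text and a chart review before enrolment, with no additional visit or examination. The position results may look slightly less favourable.

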9. PARTICIPANT SELECTION AND ENROLMENT

9.1. Identifying participants

The participants of the study are patients who had an implantation of a CT Lucia 601 lens at least six months earlier. This could be for different reasons such as a complicated cataract surgery, a posterior capsule tear during vitrectomy or an explantation of an in-the-bag lens with placement of a sulcuslens.

The patients will be contacted by the study nurse to inform them about the study and its purpose. An information brochure and a copy of the informed consent will be sent to the patient after this informative call to allow to read the information through at home. About 1-2 weeks later, after receiving the informed consent form, the patients will receive a second call to ask for final approval or disapproval to be enrolled in the trial and to make one visit in het hospital for some postoperative non-invasive examinations.

9.2. Consenting participants

Patients that had an implantation of the CT Lucia 601 at least 6 months ago, will receive a phone call of the study nurse and will receive an informed consent at home. After 2 weeks the study nurse will make a second call to ask the patients to participate in the clinical trial. Per patient, both eyes will be eligible for inclusion in the study. The contralateral eye without CT Lucia 601 will be used to create a control group.

Following the guidelines of the Ethics Review Committee of the World Health Organisation (WHO ERC), potential participant must personally sign and date the latest approved version of the informed consent form before any clinical investigations are performed.

Written and verbal versions of the participant information and Informed consent will be presented to the participants detailing no less than: the exact nature of the clinical investigation; the implications and constraints of the clinical investigation plan; the known side effects and any risks involved in taking part. It will be clearly stated that the participant is free to withdraw from the clinical investigation at any time for any reason without prejudice to future care, and with no obligation to give the reason for withdrawal.

The participant will be allowed as much time as wished to consider the information, and the opportunity to question the Investigator, their GP or other independent parties to decide whether they will participate in the clinical investigation. Written Informed Consent will then be obtained by means of participant dated signature and dated signature of the person who presented and obtained the informed consent. The person who obtained the consent must be suitably qualified and experienced, and have been authorised to do so by the Coordinating/Principal Investigator. A copy of the signed Informed Consent will be given to the participants. The original signed form will be retained at the clinical investigation site.

In case of updates of the participant information and Informed consent the participant must personally sign and date the latest approved version of the informed consent form before any further clinical investigation specific procedures are performed.

For this clinical trial, signature for approval from the patient will be obtained at the appointment in the hospital on the date agreed with the study nurse.

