8. CLINICAL INVESTIGATION POPULATION

8.1. Number of participants

A total of 100 patients will be included.

Estimated enrolment time is 12 months

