13. STATISTICS

13.1. Description of statistical methods

The results from this clinical investigation will be presented with descriptive statistics. No hypothesis testing is planned for this investigation.

For continuous variables (ex: age)

In case, the data follow of a normal distribution the T-Test will be applied and the data will be reported as the means and standard deviations by group. Otherwise a signed-rank test of Wilcoxon will be performed and the data will be report as the medians and interquartile ranges.

For count data, the Pearson's Chi² test will be applied to compare the groups and the data will be reported by counts and proportions by group.

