13.2. The number of participants

Given the exploratory nature of the trial, 100 patients will be recruited by group.

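### The plan admits both eyes of a patient and draws controls only from fellow eyes without the lens, but defines no unit of analysis and no rule for patients with the lens in both eyes.

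*Combined protocol and SAP*

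**What the plan says.** All references are to the combined protocol and SAP.

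- **Eligibility (9.2).** "Per patient, both eyes will be eligible for inclusion in the study". The next sentence defines the comparison group: "The contralateral eye without CT Lucia 601 will be used to create a control group".
- **Size.** Section 8.1: "A total of 100 patients will be included". Section 13.2: "Given the exploratory nature of the trial, 100 patients will be recruited by group". Both count patients.
- **Methods (13.1).** For continuous data: "In case, the data follow of a normal distribution the T-Test will be applied", with no statement of whether it is paired. "Otherwise a signed-rank test of Wilcoxon will be performed", which is a paired test. For categorical data: "For count data, the Pearson's Chi² test will be applied to compare the groups", a test for independent observations, and "the data will be reported by counts and proportions by group". The same section opens by saying that the results are descriptive and that no hypotheses will be tested.
- **Analysis set (13.7).** This section says only which patients will be approached.

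No section says whether the unit is the patient or the eye, which eye counts when both carry the lens, or how correlation between the eyes of one patient is handled. Sections 8.2 and 8.3 do not exclude patients with the lens in both eyes.

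**The concern.** The eligibility rule in 9.2 and the tests in 13.1 do not fit together for a patient with the lens in both eyes. Both eyes qualify as study eyes, and neither qualifies as a control.

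- The chi-square test would take the two study eyes as separate independent observations.
- The signed-rank test needs a study eye and a control eye from the same person, so it cannot use this patient.
- Summaries by group and paired comparisons can therefore rest on different patients without the reader being told.

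The primary endpoint is whether the lens can be used safely in the sulcus (section 4), so the denominator of each complication rate matters. As written, one analyst could divide by patients and another by eyes. A complication in both eyes of one person could be reported as one event or two.

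Such patients are foreseeable. Section 8.2 includes lens exchange for opacification or intolerance, and section 5 links intolerance mainly to multifocal lenses. That these reasons can affect both eyes is an inference, not a statement in the plan.

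**Working it through.** **The plan's own figure.** The 100 cannot be re-derived, because no effect size, standard deviation, power or precision target is given. For orientation, 100 against 100 independent eyes detect (1.960 + 0.842) × √(2/100) = 0.40 SD with 80% power at the two-sided 5% level of section 13.3.

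**Inputs.** 100 patients (8.1). B, the number with two study eyes, and ρ, the correlation between the eyes of one patient, are not in the documents and are assumed. Every other patient is assumed to supply one control eye.

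**Group sizes.** Study eyes n1 = 100 + B; control eyes n2 = 100 - B. The totals in 8.1 and 13.2 agree only if B = 0, so that each patient gives one eye to each group.

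**Study-eye estimates.** The design effect for a mean or proportion over all study eyes is D = 1 + 2Bρ/n1. The true standard error is √D times the naive one; the naive one is too small by 1 - 1/√D.

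| B | Study / control eyes | ρ | D | True SE larger by | Naive SE too small by |
|---|---|---|---|---|---|
| 10 | 110 / 90 | 0.5 | 1 + 10/110 = 1.091 | 4% | 4% |
| 10 | 110 / 90 | 1.0 | 1 + 20/110 = 1.182 | 9% | 8% |
| 20 | 120 / 80 | 0.5 | 1 + 20/120 = 1.167 | 8% | 7% |
| 20 | 120 / 80 | 1.0 | 1 + 40/120 = 1.333 | 15% | 13% |

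At ρ = 0.5, a nominal 95% interval that ignores the clustering would cover 93.9% (B = 10) or 93.0% (B = 20). A correlation of 1.0 is an upper bound. It would be reached if the single quality-of-vision score in 11.1, which is not said to be per eye, were entered for both study eyes.

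**Study eyes against fellow eyes, unpaired test.** With equal variances and the same ρ for every pair of eyes:

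- naive variance = 1/n1 + 1/n2
- true variance = 1/n1 + 1/n2 + 2Bρ/n1² - 2ρ/n1

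The last two terms combine to 2ρ(B - n1)/n1² = -200ρ/n1². This is negative for any positive ρ, so the naive variance is too large and the test is conservative.

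- B = 10, ρ = 0.5: naive 0.02020; true 0.02020 - 100/12,100 = 0.01194; true type I error 1.1%.
- B = 20, ρ = 0.5: naive 0.02083; true 0.02083 - 100/14,400 = 0.01389; true type I error 1.6%.
- B = 0, ρ = 0.5: true type I error 0.6%.

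In this comparison the ignored pairing outweighs the double study eyes. With pairing used, 100 pairs at ρ = 0.5 detect (1.960 + 0.842) × √(2 × 0.5/100) = 0.28 SD, against 0.40 SD without it.

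**The case against.** The two sentences in 9.2 can be read together as one study eye and one control eye per patient. Sections 8.1 and 13.2 then agree exactly. That reading is plausible, but it still gives no rule for a patient whose fellow eye also carries the lens.

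The number of such patients may be near zero. Section 5 puts capsule breaks at about 1 in 500 operations, so bilateral cases by that route should be uncommon. This stands as a limit on the size of the problem; the lens-exchange route remains open, and no figure is given for it.

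Section 13.1 plans means, medians, counts and proportions, and no standard error or confidence interval for a study-group rate. That also stands: the 4% to 15% applies only to whatever standard error or interval is eventually reported.

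Section 13.6 leaves the final statistical plan to be agreed before data lock. That makes the correction easy, but it does not supply the missing rule.

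Two stronger readings are tempting. A reader might infer that the plan analyses eyes as independent observations and so counts bilateral patients twice. No section says so: the unit is undefined, and the named tests are mixed. A reader might also infer that the between-eye comparison would give too many false positives. Under the assumptions above it would give too few.

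**Conclusion.** The gap is real and modest. Section 9.2 admits both eyes and restricts controls to fellow eyes without the lens. Section 13.1 names tests with conflicting requirements and no unit of analysis. A bilateral patient fits none of this cleanly: the eyes are not independent, as the chi-square test needs, and form no study-control pair, as the signed-rank test needs.

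The size depends on two assumed quantities. For 10 to 20 bilateral patients in 100 and a correlation of 0.5 to 1.0, the true standard error of a study-eye estimate exceeds the naive one by 4% to 15%; equivalently, the naive one is about 4% to 13% too small. With few bilateral patients the numerical effect is small, and what remains is an ambiguous denominator for the safety rates. The documents do not support a claim that precision has already been overstated.

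**What to change.** In 9.2 and 13.1, state the unit of analysis and choose one of two routes:

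1. One prespecified study eye per patient for the main estimates, with second study eyes, including their adverse events, tabulated separately.
2. All study eyes, with errors clustered by patient (for example GEE or a mixed model).

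Under either route, limit the comparison of study and control eyes to patients with exactly one implanted eye and use paired methods: paired t-test, signed-rank test, and McNemar's test in place of Pearson's chi-square. Give the numbers of patients and of eyes in every table, and reconcile 8.1 with 13.2.

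The cost is a few sentences, which can go into the plan that 13.6 requires before data lock. The first route takes second eyes of bilateral patients out of the main estimate, which is why their events need their own table. Under both routes the between-eye comparison omits bilateral patients, so it still rests on a different set from the main estimates; the counts make that visible but do not remove it.

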5. INTRODUCTION

Preface

In Belgium, approximately 120 000 cataract surgeries are performed annually. During this surgery, the lens is removed from its bag, and replaced by an intra-ocular lens (IOL). Older types of IOLs are made from non-foldable PMMA, requiring to make a large incision the eye. Modern types of IOLs are made from foldable acrylic material, allowing the insertion of the IOL through an incision as small as 1.8 mm. Preferably, the IOL is inserted in the lens bag, but in approximately 1 in 500 surgeries, a break of the posterior lens capsule occurs. When this complication occurs, it may not be possible anymore to use an in-the-bag implantation. In this case, the IOL can be inserted in front of the anterior lens bag (and behind the iris), which is named "in-the-sulcus" implantation. If no lens capsule is available, as a last resort the IOL can be clipped on the anterior side of the iris, using a dedicated "irisclaw" IOL. Such complicated surgeries are usually referred to the vitreoretinal department in third-line care centers. In our center, we treat such referred complicated cases weekly.

Another condition where implantation of an IOL in the sulcus may be required is when the implanted IOL (in the bag) opacifies or is not tolerated by the patient (mostly in case of multifocal IOL). In such case, the IOL is usually removed from the bag and replaced by an IOL in the sulcus.

Requirements of sulcus IOLs

For optimal performance and stability, the following properties are preferred for an IOL that is inserted in the sulcus:

- A relatively large optical part of ≥ 6 mm to avoid entrapment of the pupil behind the optic of the IOL
- An angulated IOL design that brings the optic of the IOL backward in order to avoid contact with the posterior side of the iris and also to avoid entrapment of the pupil
- A large IOL total diameter, since the diameter of the sulcus is larger than the lens bag
- A design of the IOL haptics that created a large contact area between the IOL and the sulcus
- A preloaded IOL system to avoid contamination of the IOL before and during insertion that could lead to postoperative infection (endophthalmitis). The use of a preloaded system is nowadays considered as the most effective preventive measure to avoid such serious complication.

Availability of sulcus IOLs

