10 INVESTIGATIONAL DEVICE

10.1. Investigational device details

CT LUCIA hydrophobic C-loop IOL: CT Lucia® 601P

- Hydrophobic acrylic
- Heparin coated surface
- Preloaded system (avoiding contamination and minimizing risk of endophthalmitis)
- Off-label used for 'in the sulcus' implantation

Easy handling properties:

- unfolds very slowly after insertion in the eye: time for positioning IOL haptics

Perfect 'in the sulcus' design: good centration and positioning postoperative

- large optical part of ≥ 6 mm to avoid entrapment of the pupil behind the optic
- angulated IOL design that brings the optic backward to avoid contact with iris or entrapment of pupil
- IOL haptics make large contact between IOL and the sulcus

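### The control eye is defined by lens model, although the primary question is about this lens in the sulcus; study and control eyes should be defined by lens position as well

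*Combined protocol and SAP*

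**What the plan says.** The primary endpoint in section 4 is to "determine whether the CT Lucia 601 IOL can be used safely in the sulcus". Section 10.1 lists that position as "Off-label used for 'in the sulcus' implantation", and the introduction states the usual position: "Preferably, the IOL is inserted in the lens bag".

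Section 9.2 builds the comparison: "Per patient, both eyes will be eligible for inclusion in the study", followed by "The contralateral eye without CT Lucia 601 will be used to create a control group". No other section defines the control group. Section 13 refers to groups without saying what they are.

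In section 8.2, the first two inclusion routes require sulcus placement. The third, lens exchange, names the model but not the position. Sections 9.1, 9.3 and 13.7 describe the patients to be approached by lens model alone. The introduction adds that, before this lens, the centre used another one "that was certified for use in the sulcus".

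**The concern.** The outcomes in section 6 (lens position, flare and pigment, pressure, aberrations) are ones that sulcus placement could affect. A comparison meant to inform safety in the sulcus needs controls whose position is known and is not the sulcus. The rule in 9.2 sets only the lens model, with two consequences:

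- It shuts out as controls the fellow eyes that have the same lens in the bag, and the surrounding text leaves room to count them as study eyes. In-the-bag results would then enter a sulcus safety summary.
- It lets in fellow eyes with another sulcus lens and mixes them with the rest. Those eyes share the position under study, so position-related differences are pulled toward zero. In a safety study that error is in the reassuring direction.

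**Working it through.** **Step 1: apply the wording to each kind of fellow eye.** No figure in the plan depends on this rule, so there is nothing to reproduce.

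| Fellow eye | Control under 9.2? | Study eye under 8.2? | What the pair contrasts |
|---|---|---|---|
| CT Lucia 601 in the bag, not from an exchange | No | Fits none of the three routes, but 9.1, 9.3 and 13.7 recruit by model and 9.2 admits both eyes | Position, same model |
| CT Lucia 601 in the bag after lens exchange | No | Yes, on the wording of the third route | Position, same model |
| Different lens in the sulcus | Yes | No | Model, same position |
| Different lens in the bag | Yes | No | Model and position together |
| Natural lens still present | Yes | No | Implant against no implant |
| CT Lucia 601 in the sulcus | No | Yes, if it came by one of the routes | None: two study eyes |

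The first two rows are the only ones that hold lens model, material and coating constant while position differs. Surgical history may still differ between the eyes, so even these pairs do not isolate position completely. The third row is pooled with the fourth and fifth. The exclusion criteria in 8.3 do not name a sulcus lens in the fellow eye and are not said to apply to control eyes.

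**Step 2: dilution from the third row.** Let D be the true mean difference between sulcus and non-sulcus eyes, and g the share of controls with another sulcus lens that has the same position-related effect. The expected observed difference is (1 − g) × D. At g = 10% it is 0.90 D; at g = 20% it is 0.80 D. This holds for a purely descriptive comparison.

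**Step 3: precision lost from the first two rows.** Take 100 pairs as the starting point (section 8.1 plans 100 patients) and let a share f of fellow eyes be barred. The width of a 95% interval is proportional to t(0.975, n − 1)/√n with n = 100 × (1 − f). Relative to n = 100:

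- f = 10%, n = 90: 6% wider
- f = 20%, n = 80: 12% wider
- f = 30%, n = 70: 20% wider

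**Step 4: the same on the power scale, for illustration.** The plan has no power basis, so assume a paired t-test, two-sided 5% (section 13.3), 100 pairs and 80% power. That corresponds to 0.283 SD of the paired differences.

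- Barred eyes, f = 10%, 20%, 30%: power 75.6%, 70.5%, 64.6%.
- Dilution, g = 5%, 10%, 20% (effect 0.283 × (1 − g), n = 100): power 75.9%, 71.3%, 61.1%.
- Dilution at lower shares, g = 0.2%, 1%, 2%: power 79.8%, 79.2%, 78.4%.

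The share of 0.2% comes from the introduction's rate of posterior capsule break, about 1 in 500 surgeries (1/500 = 0.2%). It is not a fellow-eye rate: lens exchange is another route to the sulcus, and risk may be correlated between a patient's eyes. It is the nearest figure the documents offer, and 5% is 25 times as high.

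**The case against.** The strongest reply is that the affected eyes may be few or absent. No section says that anyone put a CT Lucia 601 in the bag of a fellow eye. The introduction describes the centre's use of it in the sulcus, and since complicated cases are usually referred in, the fellow eye's lens may have been chosen elsewhere. The remark that "this new design allows easier implantation in the bag" is about the successor model and is not evidence of in-the-bag use of the 601. Other sulcus lenses in fellow eyes may also be rare. This stands, and it limits the size of the point.

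It can also be said that choosing a comparator is a matter of judgement. The question concerns this model in this position, so a fellow eye with a certified sulcus lens is a legitimate reference for the model. That stands too. The fault is pooling such an eye, unlabelled, with non-sulcus controls.

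A reader might infer that the data of an in-the-bag CT Lucia 601 fellow eye are lost altogether. The documents do not support that: such an eye is barred from the control role only, and the model-based wording could admit it as a study eye. A reader might also take the power figures as the plan's expected loss. They cannot be, because section 13.1 says no hypothesis testing is planned (though it then names tests), section 13.2 gives no power basis, and the 80% starting point is assumed.

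Finally, section 9.1 speaks of a sulcus lens after explantation, so the third route was probably meant to require the sulcus. Section 8.2 does not say so, and eligibility is decided there.

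**Conclusion.** The point holds as a misalignment between a stated rule and the primary question. The only control definition selects on model; read literally, it excludes same-lens in-the-bag fellow eyes, admits other sulcus lenses, and is corrected nowhere else. The direction of the dilution is clear if another sulcus lens carries similar position-related effects: toward no difference.

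The size is unknown. At shares of 2% or less the dilution is negligible; at 10% to 20% it would matter, and the documents support neither range. The case for acting rests on the definition and the low cost of repair, not on a demonstrated loss of power.

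**What to change.** In 8.2 (and its copy in section 4), state that the study eye is an eye with a CT Lucia 601 in the sulcus, for all three routes. In 9.2, define the control eye as the contralateral eye without an intra-ocular lens in the sulcus. In-the-bag CT Lucia 601 fellow eyes, including those from a lens exchange, then serve as controls and not as study eyes.

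For the analysis:

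- Report pairs with an in-the-bag CT Lucia 601 fellow eye as a named subset.
- Report pairs whose fellow eye has a different sulcus lens separately, as a comparison of lens models, and keep them out of the pooled controls. Their study eyes stay in the study-eye results.
- Record lens model, position and lens status for both eyes. The new definition still admits eyes with a natural lens, no lens or an iris-claw lens, so readers need to see the mix.

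The cost is a one-sentence edit in each of 8.2 and 9.2, the matching line in the summary, a few form fields and a descriptive table. It calls for no extra patients or visits. The downside is that a few pairs leave the pooled between-eye comparison.
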